3. POSTOPERATIVE PHASE**RECOVERY**

- If VAS >4: 1g Paracetamol IV
- Reevaluation after 30min.
 - If VAS >4: 2,5mg Piritramide IV

APPENDIX VI VAS scale

APPENDIX VII: Participant's pain log book

NOTABLE trial

First & last name:	
Date of surgical procedure:	

Arrival at home:

Time of arrival at home:

Pain score:

0	1	2	3	4	5	6	7	8	9	10

Pain medication:

	Dose in mg	Number of tablets	Time intake
Paracetamol			
Ibuprofen			
Other			

Day 1 after surgery:

Pain score morning:

0	1	2	3	4	5	6	7	8	9	10

Pain score evening:

0	1	2	3	4	5	6	7	8	9	10

Pain medication:

	Dose in mg	Number of tablets	Time intake
Paracetamol			
Ibuprofen			
Other			

Day 2 after surgery:

Pain score morning:

0	1	2	3	4	5	6	7	8	9	10

Pain score evening:

0	1	2	3	4	5	6	7	8	9	10

Pain medication:

	Dose in mg	Number of tablets	Time intake
Paracetamol			
Ibuprofen			
Other			

Day 3 after surgery:

Pain score morning:

0	1	2	3	4	5	6	7	8	9	10

Pain score evening:

0	1	2	3	4	5	6	7	8	9	10

Pain medication:

	Dose in mg	Number of tablets	Time intake
Paracetamol			
Ibuprofen			
Other			

Day 4 after surgery:

Pain score morning:

0	1	2	3	4	5	6	7	8	9	10

Pain score evening:

0	1	2	3	4	5	6	7	8	9	10

Pain medication:

	Dose in mg	Number of tablets	Time intake
Paracetamol			
Ibuprofen			
Other			

Day 5 after surgery:

Pain score morning:

0	1	2	3	4	5	6	7	8	9	10

Pain score evening:

0	1	2	3	4	5	6	7	8	9	10

Pain medication:

	Dose in mg	Number of tablets	Time intake
Paracetamol			
Ibuprofen			
Other			

Day 6 after surgery:

Pain score morning:

0	1	2	3	4	5	6	7	8	9	10

Pain score evening:

0	1	2	3	4	5	6	7	8	9	10

Pain medication:

	Dose in mg	Number of tablets	Time intake
Paracetamol			
Ibuprofen			
Other			

Day 7 after surgery:

Pain score morning:

0	1	2	3	4	5	6	7	8	9	10

Pain score evening:

0	1	2	3	4	5	6	7	8	9	10

Pain medication:

	Dose in mg	Number of tablets	Time intake
Paracetamol			
Ibuprofen			
Other			

APPENDIX VIII: Dyspareunia questionnaire

PAIN
LOCATION AND INTENSITY

1) Do you experience pain during sexual activity? Yes / No

2) If yes, where do you experience pain during sexual activity? Is there a specific place?

- a) at the vaginal opening
- b) at the *labia majora* (major lips)
- c) in the vagina
- d) in the pelvic or abdominal region

3) Please classify the intensity of the pain at the entrance and/or the first part of the vagina on the scale below from 0 to 10?.

0	1	2	3	4	5	6	7	8	9	10
No										worst
pain										pain ever

3) Please classify the intensity of the pain in the pelvic or abdominal region on the scale below from 0 to 10?

0	1	2	3	4	5	6	7	8	9	10
No										worst
pain										pain ever

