1.6. Objectives of the NOTABLE Trial

Is a vNOTES adnexectomy at least as effective compared to the standard transabdominal laparoscopic approach (LSC) for removing a benign adnexal mass without spill?

Secondary research questions are:

- Do more women treated by vNOTES prefer to leave the hospital on the day of surgery compared to LSC?
- Do women treated by vNOTES suffer from less pain compared to women treated by LSC in the first postoperative week?
- Is the removal of a benign adnexal mass by vNOTES faster compared to LSC?
- Does a vNOTES cause more pelvic infection or other complications compared to LSC?
- Does a vNOTES result in more hospital readmissions during the first six weeks following surgery compared to LSC?
- Does a vNOTES approach result in more women reporting dyspareunia, less quality of life or less sexual wellbeing at 3 or 6 months after surgery when compared to women treated by LSC?
- What are the costs of a vNOTES compared to LSC?

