3.2. Determining eligibility

All women regardless of age and parity presenting with a symptomatic or asymptomatic persistent benign adnexal mass on clinical examination who provide consent to participation are eligible in the NOTABLE trial based on the findings of the ultrasound findings and will be randomised before the procedure.

The following inclusion/exclusion criteria will be applied to assess eligibility:

Inclusion criteria:

- All women regardless of age and parity with a symptomatic adnexal mass presumed to be benign based on ultrasound examination by applying the IOTA simple rules
- All women regardless of age and parity with an asymptomatic persistent adnexal mass presumed to be benign based on ultrasound examination by applying the IOTA simple rules

- Written informed consent obtained prior to surgery

Exclusion criteria:

- History of hysterectomy by any technique
- History of rectal surgery
- Suspected rectovaginal endometriosis
- Suspected endometriotic cyst
- Solid adnexal mass
- High suspicion of adnexal malignancy based on clinical, ultrasound or biochemical findings
- History of pelvic inflammatory disease, especially prior tubo-ovarian or pouch of Douglas abscess
- Active lower genital tract infection e.g. Chlamydia, N. gonorrhoeae
- Virginity
- Pregnancy
- Need for other uterine surgical intervention (i.e. endometrial ablation, resection, myomectomy or hysterectomy)
- Additional pathology necessitating hysterectomy
- Failure to provide written informed consent prior to surgery

Obesity (Body Mass Index or BMI > 30), nulliparity or large diameter of the cyst are not considered to be an exclusion criterion per se. We will only stratify for the diameter of the cyst because this parameter was perceived by the gynaecological surgeon as the most important one to influence the difficulty of the procedure. Stratification for three parameters in a small pilot randomised trial with a limited number of participants is not sensible.

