- Postoperative pain defined by the total use of analgesics during the first week following surgery as described in the standardized pain treatment protocol, as an ordinal outcome. The use of pain medication following surgery should be reported in the nursing file. At home the participants should note in their participant log book the name, dosage, route of administration of any analgesic drug that was taken from the moment they are at home until the assessment on day 7 irrespective of whether this was done on their own initiative or after consulting a family physician or any other medical specialist. The assessment of the total use of analgesics will be done on day 7 by the outcome assessor (the coordinating investigator), who is blinded for the intervention done by the principal investigator.
- Postoperative infection defined by lower abdominal pain with fever $> 38^{\circ}\text{C}$ and positive clinical signs or laboratory findings, detected during the first six weeks of surgery, as a dichotomous outcome.
- Per- or postoperative complications according to the Clavien- Dindo classification detected during the first six weeks of surgery, as a dichotomous outcome (Appendix III).
- Hospital readmission during the first six weeks of surgery, as a dichotomous outcome.
- Incidence and intensity of dyspareunia recorded by the participants at 3 and 6 months by self-reporting using a simple questionnaire and VAS scale, as a dichotomous and ordinal

outcome. A measurement of the prevalence and the intensity of dyspareunia will be done at baseline assessment.

- Sexual wellbeing at baseline, at 3 and 6 months by self-reporting the SSFS.
- Quality of life at baseline, at 3 and 6 months by self-reporting the EQ-5D-3L questionnaire.
- Duration of surgery measured as the time in minutes from the insertion of the bladder catheter to the end of vaginal/abdominal wound closure, as a continuous outcome.

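### The dyspareunia form has no answer for women without sexual activity or who avoid it because of pain, so a No is ambiguous and dyspareunia after colpotomy may be undercounted

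*Protocol*

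**What the plan says.** Protocol section 1.6 makes this a research question about harm: "Does a vNOTES approach result in more women reporting dyspareunia, less quality of life or less sexual wellbeing at 3 or 6 months". Section 5.3 defines the outcome as "Incidence and intensity of dyspareunia recorded by the participants at 3 and 6 months by self-reporting using a simple questionnaire and VAS scale", dichotomous for incidence and ordinal for intensity, and adds "A measurement of the prevalence and the intensity of dyspareunia will be done at baseline assessment".

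The form is printed in Appendix VIII. It opens with "Do you experience pain during sexual activity? Yes / No" and continues with "If yes, where do you experience pain during sexual activity? Is there a specific place". Two 0-to-10 intensity scales follow, with no condition tying them to the answer to item 1. Nothing on the form asks whether the woman is sexually active or, if not, why. No recall period is given.

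Entry is open to "All women regardless of age and parity with a symptomatic adnexal mass presumed to be benign based on ultrasound examination" (section 3.2), with a parallel criterion for asymptomatic persistent masses. Virginity is excluded, but current sexual activity is not required. Sections 4.1.1 and 4.1.2 tell women in both arms to abstain from intercourse for six weeks.

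The SSFS (Appendix IX) is given at baseline, 3 and 6 months with a three-month recall, but section 5.3 lists it for sexual wellbeing. Its item 7 has categories for painless penetration, painful penetration, penetration formerly but no longer possible, and penetration never achieved.

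Section 6.3.3 imputes a single missing item from the other answers. It does not impute when more than one item or the whole form is missing.

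**The concern.** A woman with no sexual activity at 3 or 6 months has no truthful box on item 1. She can tick No, or leave it blank. Ticked No, she cannot be told apart from a woman who is active and free of pain. If she is inactive because sex hurts or she fears that it will, she is a case that the question in section 1.6 is meant to find, and the form either records her as unaffected or loses her.

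This matters because the vaginal incision belongs to one arm. Inactivity unrelated to surgery should balance across arms and mainly shrinks the absolute difference. Avoidance because of pain could differ by arm, and then the form would miss part of the harm in the arm where it arises.

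The absent recall period adds to the ambiguity. Some women may not have resumed intercourse by 3 months, and an answer could refer to the time before surgery. One trial summarised in section 1.4.1 reported dyspareunia once intercourse was resumed; this form cannot make that distinction.

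**Working it through.** **Stated figures.** The protocol gives no expected dyspareunia rate, no share of women without sexual activity and no power for this outcome, so there is nothing to reproduce. The only indication of age is the investigators' own series of 20 women (Appendix I: mean 51 years, range 31 to 75). Inactive women can therefore be enrolled, but their number is unknown.

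**What each answer leads to**

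| Woman's situation | Ticks No | Leaves item 1 blank |
|---|---|---|
| Active, no pain | correct | not applicable |
| Inactive, other reason | counted with the pain-free | missing if more items are blank; if only item 1 is blank, imputed from the rest (an intensity of 0 could plausibly give No) |
| Inactive because of pain | counted with the pain-free | same, and the pain is lost |

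**Does the SSFS fill the gap?** In part. Item 7 catches painful penetration, item 7a grades it, and a woman who stopped because of pain could choose the category for no longer possible. But item 7 has no category for no activity and does not give pain as the reason for stopping. Items 3 to 5 presuppose sex with a partner, and the only answer for non-activity is in item 6, on masturbation.

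**Size, on assumed rates.** Let *p* be dyspareunia among active women (assumed 25% vNOTES, 10% laparoscopy), *u* the share inactive for other reasons (assumed 10%, 30%, 50%, equal in both arms) and *a* the share avoiding sex because of pain.

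- Inactive women tick No: recorded rate = (1 − u − a) × p
- Inactive women leave the form blank: rate among responders = p
- Dyspareunia or avoidance because of pain, over all women: (1 − u − a) × p + a

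*No avoidance because of pain (a = 0).* If inactive women tick No, the difference is (0.25 − 0.10) × (1 − u):

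- u = 10%: 0.15 × 0.90 = 13.5 points
- u = 30%: 0.15 × 0.70 = 10.5 points
- u = 50%: 0.15 × 0.50 = 7.5 points

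If they leave the form blank, the difference stays at 15 points among responders.

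*Avoidance because of pain in 10% of vNOTES women and none of the laparoscopy women (also assumed).*

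| u | Recorded if inactive women tick No | Dyspareunia or avoidance, all women |
|---|---|---|
| 10% | 0.80 × 0.25 − 0.90 × 0.10 = 11.0 points | 0.300 − 0.090 = 21.0 points |
| 30% | 0.60 × 0.25 − 0.70 × 0.10 = 8.0 points | 0.250 − 0.070 = 18.0 points |
| 50% | 0.40 × 0.25 − 0.50 × 0.10 = 5.0 points | 0.200 − 0.050 = 15.0 points |

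The gap is 10 points in each row, exactly the avoidance share. If these women leave the form blank, responders again show 15 points and the avoiders appear nowhere.

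**The case against.** A reader might infer that the protocol counts inactive women as free of dyspareunia, and that harm from the colpotomy is therefore undercounted. The documents do not support that. No section codes an inactive woman as No. One who leaves several items empty is missing under section 6.3.3, and the rate among active women is then not diluted.

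The simple dilution is also less damaging than the point differences suggest. With a = 0 the risk ratio stays at 2.5 throughout, and the ability to see a difference hardly changes. Take 33 women per arm (66 / 2, section 6.1) and SE = √{[p₁(1 − p₁) + p₂(1 − p₂)] / n}. At 10% inactive, difference/SE is 0.135 / 0.0881 = 1.53 with inactive women as No (n = 33), against 0.150 / 0.0967 = 1.55 among active women only (n = 29.7). At 30% the pair is 1.32 and 1.37; at 50% it is 1.09 and 1.16. What does harm is differential avoidance because of pain, and nothing in the protocol shows how common that would be. Mock incisions blind the participants (section 4.1), so mere knowledge of a vaginal wound should not drive avoidance in one arm.

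Coding rules and denominators may properly sit in a statistical analysis plan, which was not available here. That stands as far as it goes, but a plan can only work on what the form collects, and this form does not record who was active or why not.

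Finally, incidence among active women is not a safe main analysis. Activity arises after randomisation, and restricting to active women removes precisely those who avoid sex because of pain. That objection stands in full and shapes the fix.

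**Conclusion.** The point holds in conditional form. Appendix VIII item 1 cannot separate active women without pain from inactive women and cannot identify women who avoid sex because of pain, and SSFS item 7 makes up for this only in part. Dyspareunia after colpotomy may therefore be undercounted; that it will be is not shown.

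On the assumed rates, a 15-point difference is recorded as anything from 7.5 points (half the women inactive, all ticking No) to the full 15 (all leaving the form blank). If 10% of vNOTES women alone avoid sex because of pain, those 10 points are missed when they tick No, and the women drop out when they leave the form blank. Every rate here is an assumption.

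This is a secondary outcome in a small pilot trial, and the primary non-inferiority result is untouched. It is a low-cost improvement to a safety measure, worth making because what the form does not collect cannot be recovered later.

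**What to change.** At baseline, 3 and 6 months, ask item 1 for a stated period with four answers: Yes; No; no sexual activity because of pain or fear of pain; no sexual activity for another reason. Choose the period for the 3-month form with the six weeks of advised abstinence in mind.

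Compare the arms on dyspareunia or avoidance because of pain, and state the denominator; using all women who answer avoids selecting on activity after randomisation. Show by arm how many are inactive for other reasons. Give incidence among sexually active women only as a supporting description.

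The cost is one or two extra tick boxes on the study's own form and one extra tabulation. No visit or additional questionnaire is needed, and the SSFS stays as it is.

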1.4. Literature review

1.4.1 Systematic Review

Health technology assessment (HTA) of surgical interventions requires an initial evaluation of the safety and feasibility followed by randomised controlled trials of effectiveness. We conducted a comprehensive systematic review on the efficacy of colpotomy in the treatment of benign adnexal mass. After searching three electronic databases (MEDLINE, EMBASE and The Cochrane Library) from inception to 1 August 2015 using 'colpotomy' and 'adnexal diseases' or 'adnexal mass' as MeSH terms or key words, ten citations were identified, of which a total of four studies were eligible for inclusion. Two studies were observational including one very small case series (7 women) and one prospective cohort study (257 women); two studies were randomised controlled trials (66 women and 79 women respectively).

A summary of the evidence is given below:

We retrieved one observational study from Korea (14). The authors performed transvaginal NOTES in seven women with adnexal masses through a 2-cm incision in the posterior vaginal fornix. A transvaginal NOTES system comprising a wound protractor and a surgical glove with sheaths was used. Resection was performed according to the method of standard laparoscopic adnexal surgery. The adnexal mass was removed via the incision of the posterior vaginal fornix after complete resection. Since June 2011, seven women have undergone transvaginal NOTES for adnexal masses. All cases were completed successfully without conversion to standard laparoscopic approach. The median age of the women was 48 years (range: 36–60 years) and the median body mass index was 23.6 (range: 20.4–25.3). The median tumour size was 6 cm (range: 3.7–6.7 cm). The median

operative time was 45 min (range: 40–80 min). The estimated blood loss was minimal (range: 5–300 mL). The median postoperative hospital stay was 2 days (range: 1–3 days). No postoperative complications were observed at follow-up. All women were very satisfied with the cosmetic result. The authors conclude that transvaginal NOTES may be a feasible, safe and effective surgical technique that results in excellent cosmetic results. It may be an alternative technique for the treatment of properly selected patients with adnexal masses. The authors stress the need for further clinical research.

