4. TREATMENT ALLOCATIONS

4.1. Surgical procedures

The principal investigator, who has training and experience in both laparoscopy and NOTES, will perform all surgical procedures. He is therefore not blinded. All vNOTES participants will be blinded by three superficial “mock” skin incisions similar to those routinely done with the laparoscopic technique. The wound bandages will be left in place until the day 7 postoperative control to be removed by the coordinating investigator who will state at that moment that the wound healing has left an almost invisible scar as expected. This procedure aims to blind the participants, personnel and outcome assessors. The practice of performing “mock” incisions should not be considered as unethical: it is a procedure that has already been used in some surgical trials to minimise performance and detection bias whenever a subjective outcome is measured (22). The decision to use “mock” surgery is based on the clinical equipoise regarding the balance between benefits and adverse events for the two interventions under comparison (23).

4.1.1 vNOTES adnexectomy

This is the surgical procedure done in the intervention arm of the NOTABLE trial.

Clindamycin vaginal cream is administered on admission of the study participant to the outpatient ward.

The patient is placed in lithotomy position in a vacuum mattress. The abdomen, the vulva and the vagina are disinfected with an alcoholic betadine solution and draped. A Foley catheter is inserted into the bladder.

Three superficial skin incisions are made, one deep in the umbilicus and one in the left and right iliac fossa lateral of the epigastric vessels, and in the suprapubic region. The small vertical intraumbilical skin incision is closed with a monocryl 3/0 intradermal suture. Wound bandages are applied to all three skin incisions.

A 2.5 cm posterior colpotomy is made using a cold knife. The pouch of Douglas is opened using cold scissors. A Gelpoint Mini (Applied Medical) is used as vNOTES port and is inserted into the pouch of Douglas. CO₂ is insufflated until a maximal intraperitoneal pressure of 15mmHg. An optic is inserted and the peritoneal cavity is inspected. The patient is now placed in Trendelenburg position. The small intestine is lifted out of the pelvis.

The ureter is identified, but not routinely dissected. It is only dissected if it cannot be identified transperitoneally. The proximal end of the Fallopian tube is coagulated at its origin into the uterus

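### Appendix VIII has no matching intensity scale for pain deeper in the vagina, where only the vNOTES arm has a wound

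*Protocol*

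**What the plan says.** Section 5.3 of the protocol lists among the secondary outcomes "Incidence and intensity of dyspareunia recorded by the participants at 3 and 6 months by self-reporting using a simple questionnaire and VAS scale". It treats the outcome as both dichotomous and ordinal and adds a baseline measurement of prevalence and intensity.

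The questionnaire is Appendix VIII. Item 1 asks "Do you experience pain during sexual activity? Yes / No". Item 2 asks where the pain is and offers four places: (a) the vaginal opening, (b) the labia majora, (c) the vagina, (d) the pelvic or abdominal region. Two 0-10 scales follow, both numbered 3. The first reads "Please classify the intensity of the pain at the entrance and/or the first part of the vagina"; the second reads "Please classify the intensity of the pain in the pelvic or abdominal region".

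Section 4.1.1 describes the vNOTES access: "A 2.5 cm posterior colpotomy is made using a cold knife", after which the pouch of Douglas is opened. The vNOTES case series summarised in section 1.4.1 worked "through a 2-cm incision in the posterior vaginal fornix". In the control arm (section 4.1.2) the specimen leaves through the enlarged umbilical incision, and no vaginal incision is described.

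**The concern.** The form separates the vagina from its opening and from the pelvis when it asks where the pain is, but drops that distinction when it asks how bad the pain is. A woman whose pain sits beyond the first part of the vagina can tick location (c) and then finds no scale that describes it. She can score 0 on both, leave them blank, or enter the pain under a site she has just said is not the one.

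This site matters because it is where the experimental technique leaves a wound and the control technique does not. If pain there is lost or scored 0, the intensity comparison would tend to look more favourable to vNOTES. If it is entered under another site, the total may survive, but the trial can no longer say how severe pain at the colpotomy was. Intensity that was not asked for at the time cannot be recovered later.

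**Working it through.** The protocol gives no figure to reproduce here. The check sets the location options against the scales, looks for another instrument that fills the gap, and then bounds the possible effect.

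**1. Location options (Appendix VIII, item 2) against the 0-10 scales**

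| Location option | Matching 0-10 scale |
|---|---|
| (a) vaginal opening | first scale |
| (b) labia majora | none of its own |
| (c) vagina | first scale for the first part only; none for the deeper part |
| (d) pelvic or abdominal region | second scale |

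**2. Site of the wound.** Section 4.1.1 specifies a posterior colpotomy that opens into the pouch of Douglas. The cited series places its incision in the posterior fornix. Reading the two together, the wound lies in the deeper vagina, which is the part of option (c) without a scale. Section 4.1.2 gives controls no wound there.

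**3. What is captured elsewhere**

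- Incidence: item 1 is a yes/no question with no restriction of site, so deep vaginal pain counts.
- Location: option (c) records it.
- Severity: SSFS item 7a (Appendix IX), given at baseline, 3 and 6 months, grades pain around penetration in four steps from none to severe or extreme. It names no site. It is reached only by women who answer in item 7 that penetration was possible but painful. Those for whom penetration is no longer possible, or never was, are sent to the end of the form.

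The gap is therefore in the 0-10 intensity measure by site and in nothing else.

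**4. Bounding the effect on mean intensity in the vNOTES arm**

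Inputs: 66 participants in total (section 6.1), so 66 / 2 = 33 per arm. Assumptions, not from the protocol: 4 of 33 vNOTES women (4 / 33 = 12%) have deep vaginal pain of 5/10 and no other pain, all 33 women enter the mean, and k of the 4 score 0 on both printed scales while the rest use one of them.

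Understatement of the arm mean = k x 5 / 33.

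- k = 0 (all use a printed scale): 0 / 33 = 0 points
- k = 2: 10 / 33 = 0.3 points
- k = 4 (all score 0): 20 / 33 = 0.6 points

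The mean is used only to give a sense of scale. Section 5.3 calls intensity ordinal, and the protocol states no rule for combining the two scales.

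**The case against.** The strongest reply is that little of what the trial asks depends on this scale. Section 1.6 asks "Does a vNOTES approach result in more women reporting dyspareunia, less quality of life or less sexual wellbeing at 3 or 6 months", which for dyspareunia is a question about how many women report it. Item 1 answers that for pain at any site. This stands: the incidence outcome and the stated research question are intact.

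Second, SSFS item 7a grades penetration pain at the same time points without restricting the site, and Appendix VIII supplies a location alongside it. This stands in part. The grade has four levels, belongs to the separate sexual wellbeing outcome, and is not reached by women for whom penetration has become impossible.

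Third, women with deep pain may use the pelvic or abdominal scale, so that their intensity is recorded under an imprecise label. A record with pain answered yes, option (c) ticked and 0 on both scales would also show up in the data. Both points stand, and they are why the lower end of the range is nil.

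A reader might infer that the error falls in one arm only, or that the trial under-measures its main vaginal harm. The documents support neither. Both arms complete the same form, and any woman, including a control or any participant at baseline, can tick (c) and meet the same gap. A difference between arms is plausible because only one arm has a colpotomy, but it is not demonstrated. The protocol does not rank dyspareunia above infection, complications or readmission.

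**Conclusion.** The mismatch is real and can be seen in the form itself: the vagina is offered as a location, but its deeper part has no 0-10 scale, although intensity is a named secondary outcome. The consequence is confined to that intensity measure.

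The direction of any bias is plausibly in favour of vNOTES. This assumes that pain at the colpotomy is more common in that arm and that some women score it 0 or leave it blank. The size cannot be established from the protocol. Under the assumptions shown it runs from 0 to about 0.6 points on the 0-10 scale. The assumed 12% comes from no source in the document: the in-house series (section 1.4.3) reports no complaint of pain on pelvic examination at six weeks, and the Italian randomised trial in section 1.4.1 found similar dyspareunia scores at two months. Neither rules the assumption out or supports it.

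This is a worthwhile, inexpensive improvement to one part of one secondary outcome. It does not threaten the primary analysis or the incidence comparison.

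**What to change.** Add one 0-10 item to Appendix VIII for the intensity of pain deep in the vagina, so that the intensity scales cover the vaginal location that item 2 offers. Use it in both arms at baseline, 3 and 6 months, and report it alongside the two existing scores. The duplicated item number 3 can be corrected in the same revision, as a clerical matter.

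The cost is a short amendment to the form and one more item for participants. Women already assessed will lack the new score at the time points they have passed, and the report should say so. The protocol calls the form a simple questionnaire and does not give its origin. If it was taken from an existing instrument, the added item should be identified as an addition.
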